## SYNOPSIS

Study Title	A Feasibility Study Evaluating the Impact Flexitouch Plus with Connectivity has on Compliance in Patients with Breast Cancer-Related Lymphedema (BCRL)
Protocol Date	February 11, 2021
Protocol Version	4.0
Protocol Number	4090
Name of Sponsor	Tactile Medical™
Device	Investigational Flexitouch Plus with Cellular Connectivity (FT-CC)
Study Objective	To demonstrate the feasibility of using the FT-CC to actively monitor device use data to: 
 
• Determine if patient reminders impact the rate of compliance,
 
• Identify the impact device compliance has on arm girth, quality of life, and symptoms.
 

Primary Endpoint	
 
• Compare the rate of compliance in patients treated with PASSIVE FT-CC and ACTIVE FT-CC
 

Exploratory Endpoints	
 
• Assess the impact device compliance has on arm girth
 
• Determine the impact device compliance has on measures of quality of life (QOL) and symptom assessment:           
 
◦ Lymphedema Quality of Life Tool (LYMQOL ARM)
 
◦ Short Form-36 (SF-36)
 
◦ Lymphedema Symptom Intensity and Distress Survey-Arm (LSIDS-A)
 
 
 

Study Design	This is a multi-center, on label, prospective, randomized, two-arm feasibility study.
Treatment(s)	Eligible patients will be randomized to one of the following groups for 60 days: 
 
• ACTIVE FT-CC – Text message reminders will be sent if subject does not use the device for 2 consecutive days
 
• PASSIVE FT-CC – Text message reminders will not be sent to subjects
 

Eligibility	
Inclusion Criteria:
 
 
1. Female 18 years of age or older
 
2. Diagnosis of unilateral breast cancer-related lymphedema
 
3. Willing and able to give informed consent (remotely or in-person)
 
4. Willing and able to comply with the study protocol requirements and all study-related visit requirements, including the ability to participate remotely
 
5. Willing and able to receive text messages from sponsor
 
 
Exclusion Criteria:
 
 
1. In-home use of pneumatic compression device (PCD) within previous 3 months
 

	
 
2. Phase-one complete decongestive therapy (CDT) within previous 1 month or planned phase-one CDT during study participation Phase-one CDT defined as professionally administered manual lymphatic drainage (MLD) and/or multi-layer short stretch compressive bandaging.
 
3. Inability to be fit for PCD garments
 
4. Heart failure (acute pulmonary edema, decompensated acute heart failure)
 
5. Acute venous disease (acute thrombophlebitis, acute deep venous thrombosis, acute pulmonary embolism)
 
6. Active skin or limb infection/inflammatory disease (acute cellulitis, other uncontrolled skin or untreated inflammatory skin disease) on the arms or trunk
 
7. Currently receiving treatment for cancer with curative intent.
 
8. Any circumstance where increased lymphatic or venous return is undesirable
 
9. Currently pregnant or trying to become pregnant
 
10. Known inability to receive cell phone connection where FT-CC therapy will be administered
 

Treatment Duration	60 days
Number Planned	30 Randomized Subjects

### 1.2 Site Principal Investigator Information

The sponsor will maintain a document with contact information for all investigators participating in the study. The information maintained will include full names, addresses, telephone numbers, and, if available, email addresses and mobile phone numbers for the site principal investigators and Institutional Review Board (IRB) chairperson.

## 2.0 Abbreviations

Abbreviation	Term
AE	Adverse Event
BCRL	Breast Cancer-Related Lymphedema
CDT	Complete Decongestive Therapy
CFR	Code of Federal Regulations
CRA	Clinical Research Associate
CRF	Case Report Form
CTA	Clinical Trial Agreement
DCF	Data Clarification Form
EDC	Electronic Data Capture
FDA	Food and Drug Administration
FT	Flexitouch Plus
FT-CC	Flexitouch Plus with Cellular Connectivity
GCP	Good Clinical Practice
HCPCS	Healthcare Common Procedure Coding System
ICF	Informed Consent Form
IRB	Institutional Review Board
LSIDS-A	The Lymphedema Symptom Intensity and Distress Survey-Arm
LYMQOL ARM	Lymphedema Quality of Life Tool
MLD	Manual Lymphatic Drainage
NSR	Nonsignificant Risk
PCD	Pneumatic Compression Device
PHI	Protected Health Information
PI	Principal Investigator
QoL	Quality of Life
SAE	Serious Adverse Events
SF-36	Short Form-36
UADE	Unanticipated Adverse Device Effect

## 3.0 Introduction

### 3.1 Background and Rationale

Lymphedema is a chronic debilitating disease marked by accumulation of protein rich fluid in the interstitium of the skin. Breast cancer-related lymphedema (BCRL) is a common complication from breast cancer treatment, with reported frequencies ranging from 6% to 65% (1). This insufficiency in the lymphatic system leads to limb edema in early stages and progresses to thickened skin or fibrosis over time. As a result, persons afflicted with lymphedema are prone to develop impaired extremity function, recurrent episodes of soft tissue inflammation and infection, lymphorrhea, unsatisfactory cosmesis, and a variety of psychological and social issues (2).

There is currently no cure for lymphedema, thus treatment focuses on symptom management and improved patient-reported outcomes. Using a multimodal approach, accepted interventions include: limb elevation, MLD, compression therapy, skin hygiene, and in very severe cases, lymphatic exchange (3). Pneumatic Compression Devices (PCDs) are a fairly recent addition to the armamentarium clinicians offer patients in the treatment of lymphedema. Studies have demonstrated continual use of PCDs is associated with a significant patient-reported improvement in overall symptoms, decreased limb-girth, decreased limb volume, increased elasticity of tissues, and fewer episodes of infection (4-7).

Adherence to prescribed, at-home self-care is a critical factor in the treatment of lymphedema (8-9). Research shows PCD compliance diminishes over time (10). This study seeks to determine if active monitoring of device use information and patient reminders affects compliance. Additionally, there is limited data on how various compliance rates impact health outcomes. Therefore, this study also seeks to identify the impact compliance rates have on swelling, quality of life, and symptoms.

### 3.2 Device Description

The Flexitouch Plus system (FT) (Tactile Medical™, Minneapolis, MN, USA) is an advanced pneumatic compression device clinically proven to stimulate the lymphatic system and is cleared for market in the USA (K203178, K170216, HCPCS code E0652). The device helps direct and move excess fluid from an impaired lymphatic region to healthy regions, where fluid can be absorbed and processed naturally by the body. Flexitouch Plus garment chambers inflate sequentially with each chamber inflating before the adjacent distal chamber fully deflates. This creates a dynamic wave of therapy that directs fluid into the lymphatic capillaries while maintaining distal pressure to prevent distal backflow.

The Flexitouch Plus system consists of two primary components: the controller unit and garments.

The controller unit is a programmable pneumatic compressor with four connector outlets. Each connector has eight outflow ports that garment hoses plug into. Air passes through the hoses, delivering treatment through the sequential inflation and deflation of up to 32 air chambers in the garments. By selecting the appropriate treatment program, calibrated gradient pressure is delivered to the chambers and assists in moving excess fluid out of the affected limb(s).

The air-chambered garments are made of soft, pliable fabric. They are designed to fit the contours of the body by wrapping around the limb(s) and attaching with hook and loop fasteners. A variety of upper and lower extremity treatment options are available. The pressure setting is variable between “decreased,” “normal,” and “increased.” Individual chamber pressures may also be individually adjusted.

The novel FT-CC is identical to the Flexitouch Plus with the exception of an addition of a cellular communication module to the controller unit which transmits device usage data to a cloud-based database accessible to the study sponsor. This data will be used by the sponsor to send automated text messages to subjects randomized to the FT-CC ACTIVE group that have not used their device for 2 consecutive days.

The FT-CC will be labeled, “CAUTION – Investigational Device, Limited by Federal Law to Investigational Use” and each unit will have a unique serial number. The FT-CC is investigational only in that it has the cellular communication module; in all other aspects, including cleared intended use, FT-CC is the same as the currently marketed FT.

#### 4.0 Study Objective

The objective of the study is to demonstrate the feasibility of using the FT-CC to actively monitor device use data to:

- Determine if patient reminders impact the rate of compliance
- Identify the impact device compliance has on arm girth, quality of life, and symptoms.

#### 5.0 Study Design

This is a multi-center, on label, prospective, randomized, two-arm, feasibility study (Figure 1) comparing the PASSIVE FT-CC to ACTIVE FT-CC. A multi-center design is used to expedite the enrollment period and provide a broader sample of the study population. Randomization was incorporated into the study to determine if ACTIVE FT-CC affects device use.

[figure not shown]

Figure 1. Study Design

#### 5.1 Endpoints

##### 5.1.1 Primary Endpoint

Compare the rate of compliance in patients treated with PASSIVE FT-CC and ACTIVE FT-CC

### 5.1.2 Exploratory Endpoints

To assess the exploratory endpoints, subjects will be categorized as partially compliant and compliant (Table 1). These endpoints will be analyzed using the following compliance categories.

Table 1. Compliance Category Definitions

Compliance Category	Definition
Partially Compliant	FT-CC used on average 1-4 days per week
Compliant	FT-CC used on average 5-7 days per week

- Assess the impact device compliance has on arm girth
- Determine the impact device compliance has on measures of QoL and symptoms assessment:
  - Lymphedema Quality of Life Tool (LYMQOL ARM)
  - Short Form-36 (SF-36)
  - The Lymphedema Symptom Intensity and Distress Survey-ARM (LSIDS-A)

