### 5.1.3 Outcome Measures

Primary and exploratory endpoints will be based on the outcome measures as described in Table 2.

Table 2. Outcome Measures

Endpoint	Outcome Measure
Compliance	
 
• Compare rate of compliance (# of days used/total study days) to prescribed treatment between FT-CC PASSIVE and FT-CC ACTIVE Subjects at 30 and 60 days
 

Change in Arm Girth	
 
• Comparison between baseline and day 30/60 arm girth measurement
 

Quality of Life	
 
• Comparison between baseline, 30 day, and 60 day surveys
 

Symptom Assessment	
 
• Comparison between baseline, 30 day, and 60 day surveys
 

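### Every exploratory health outcome is analysed by two compliance bands only, although each woman's use rate is recorded and the study asks about the impact of compliance rates

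*Combined protocol and SAP*

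**What the plan says.** Section 5.1.2 (Exploratory Endpoints) sets the exposure for all health outcomes: "To assess the exploratory endpoints, subjects will be categorized as partially compliant and compliant (Table 1"). After introducing the two categories it adds: "These endpoints will be analyzed using the following compliance categories". Table 1 defines the lower band as "FT-CC used on average 1-4 days per week" and the upper band as "FT-CC used on average 5-7 days per week".

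A finer measure already exists. Section 3.2 says the added module "transmits device usage data to a cloud-based database accessible to the study sponsor", and the ACTIVE arm's reminders depend on detecting two consecutive days without use. Table 2 in section 5.1.3 defines the "rate of compliance (# of days used/total study days"), but assigns it only to the comparison of the two arms at 30 and 60 days.

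Section 3.1 gives the reason for the health-outcome part of the study: "there is limited data on how various compliance rates impact health outcomes". It goes on: "this study also seeks to identify the impact compliance rates have on swelling, quality of life, and symptoms".

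Section 16.2 plans descriptive summaries and no formal tests. It names no regression, correlation or other analysis of an outcome on the use rate.

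**The concern.** There are two separate problems.

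- **Shape.** A comparison of two bands yields one difference per outcome and visit. That says whether heavier users did better on average. It does not say how outcome changes from, for example, two to four to six days a week. Within the lower band, a woman who used the device on 9 of 60 days counts the same as one who used it on 34.
- **Precision.** With about 20 women followed, precision is scarce. Replacing a near-continuous exposure by a two-level one generally widens the interval for a trend. The target of 10 in section 16.1 reads as the two randomised arms, and nothing sets the size of the compliance bands, so one of them may be small.

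Section 16.1 says the study is meant to identify which health outcomes a larger trial should use. Noisier estimates of the compliance-outcome relation make that choice less reliable.

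**Working it through.** **Inputs from the documents.** Two bands (Table 1). Rate = days used / total study days (Table 2), over 60 days of treatment. Twenty women with 60-day data, from up to 30 enrolled (section 16.1). The plan's figures agree with each other: 2 × 10 = 20, and 20 / (1 − 1/3) = 30, where the one-third loss is back-calculated. The plan states no power, effect size, use distribution or efficiency, so there is no such figure to reproduce.

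**Step 1: the bands in days.** 1 × 60/7 = 8.6, 4 × 60/7 = 34.3 and 5 × 60/7 = 42.9. The lower band is therefore 9 to 34 days and the upper band 43 to 60. Read literally, 0 to 8 and 35 to 42 days fall in neither band. Below I close the middle gap with a single cut at 4.5 or at 5 days per week, which is an assumption.

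**Step 2: shape.** Take use spread evenly over 1 to 4 and 5 to 7 days per week, and scale four relations so that each gives a band difference of −1. For the linear one, the band means are 2.5 and 6, so the slope is −1/3.5 = −0.286.

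| Relation | Band difference | Slope within lower band | Slope within upper band |
|---|---|---|---|
| Linear | −1 | −0.286 | −0.286 |
| Step at 5 days | −1 | 0 | 0 |
| Plateau after 3 days | −1 | −1.112 | 0 |
| Benefit only above 5 days | −1 | 0 | −0.999 |

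The planned contrast is the same in all four rows. That one difference can arise from any of these shapes does not depend on how use is distributed.

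**Step 3: precision, if the relation is linear.** The information kept is the squared correlation between the exposure X and its band indicator. With P the share above the cut t, m the mean and s the SD:

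kept = (E[X; X > t] − mP)² / (P(1 − P)s²)

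For a normal exposure this reduces to φ(z)² / (P(1 − P)).

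- *Normal (assumed).* 50/50: 0.3989² / 0.25 = 0.637. 80/20: 0.2800² / 0.16 = 0.490. The loss is 36% to 51%, and 20 women inform like 12.7 to 9.8. Standard errors grow by 1/√kept, a factor of 1.25 to 1.43.
- *Beta (assumed), means 0.6 to 0.8, SD 0.2 to 0.3, cut 4.5 or 5 of 7 days.* The smallest share kept is at mean 0.6, SD 0.2, cut 5, which is Beta(3, 2) with P = 0.323: (0.2653 − 0.6 × 0.3232)² / (0.3232 × 0.6768 × 0.04) = 0.583. The largest is at mean 0.8, SD 0.3, cut 4.5, with P = 0.772: 0.833. The loss is 17% to 42%, and 20 women inform like 16.7 to 11.7. Standard errors grow by a factor of 1.10 to 1.31.

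**Step 4: band size.** If a fraction q of 20 women fall in the lower band, the number there is Binomial(20, q). For q = 0.2, P(4 or fewer) = 0.0115 + 0.0576 + 0.1369 + 0.2054 + 0.2182 = 0.63. The same sum gives 0.24 for q = 0.3 and 0.006 for q = 0.5. A very small band is thus a real prospect if compliance is high, and unlikely if it is moderate.

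**The case against.** The case for leaving the plan alone has several parts.

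- **Limited purpose.** This is a feasibility study with no formal tests, and the objective in section 4.0 speaks of device compliance, with no explicit dose-response aim. This limits the consequence. It does not favour bands: section 16.2 puts the focus on estimation, and section 3.1 states the aim in terms of compliance rates.
- **A step may be true.** If benefit begins at the band edge, the bands lose little. That stands, but the protocol offers no evidence for a step, and only a display against the rate itself could suggest one.
- **Nothing is lost for good.** A reader might infer that data are thrown away. The documents do not support that: the use records and the rate remain. The loss is in the planned analysis, and an analysis on the rate chosen later would carry less weight than one specified now.
- **The size is not known.** A reader might infer a fixed loss, such as half. The documents give no use distribution. A loss of half needs, for example, an unbounded normal exposure split 80/20, whereas use is bounded at 0 to 7 days; the beta case nearest 80/20 (mean 0.8, SD 0.2, cut 4.5) keeps 0.70.
- **Small bands are not certain.** A reader might take section 16.1 to require 10 women per band. It does not. On the beta grid, the chance that the smaller band holds 3 or fewer of 20 is below 8% for means 0.6 and 0.7, and 16% to 40% only at mean 0.8.
- **Compliance is self-selected.** A slope is as open to confounding as a band difference. This is true of both and favours neither, but the report must say so.

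**Conclusion.** The point holds as a recommended improvement rather than a fatal flaw. Two facts rest on the text alone: every exploratory health outcome is to be analysed by two bands, and no analysis on the recorded rate is planned. It follows without distributional assumptions that the planned contrast cannot describe how outcome varies across compliance rates.

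The precision loss is conditional. It assumes a roughly linear relation, a single cut and a use distribution that the documents do not supply. The two assumed families in the working give overlapping ranges, with 17% the smallest loss and 51% the largest; neither end is an estimate for this trial. The exploratory, estimation-only design limits the harm, but gives no reason to prefer bands when the rate is already held.

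**What to change.** In sections 5.1.2 and 16.2, make the main exploratory analysis a regression of each Day 30 and Day 60 outcome on the average days per week of use accumulated up to that visit, adjusted for the baseline value of the outcome. Report the slope per extra day per week with a 95% confidence interval and a scatter plot. Label the result as a non-randomised, hypothesis-generating association. Keep Table 1 as a descriptive display.

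The analysis needs no new data, visits or subjects, and it includes women whose average falls in neither band.

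Costs:

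- A linear slope is assumed, and about 20 points allow only a rough check of it.
- Many slopes are estimated: one girth measure, five LYMQOL ARM scores (four domains and overall), eight SF-36 scales and at least one LSIDS-A score make 15 outcomes, or about 30 slopes over two visits. They should be read as a set, not picked singly.
- Section 5.1.2 is protocol text, so the change needs sponsor and investigator review and IRB approval under section 15.0.

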#### **5.5 Randomization Assignment and Treatment Duration**

Eligible patients will be randomized (1:1) to one of the following groups for 60 days:

- ACTIVE FT-CC – Text message reminders will be sent if subject does not use device for 2 consecutive days
- PASSIVE FT-CC – Text message reminders will not be sent to subjects

The FT-CC prescription will be a daily 60-minute U1 unilateral treatment at normal pressure. Settings and programs may be modified by the discretion of the investigator, if needed, and these modifications will be documented. If subjects are assigned to the ACTIVE FT-CC group and their device is not used for 2 consecutive days, they will receive a text message reminding them to use their device. If subjects are assigned to the PASSIVE FT-CC group, they will not receive text message reminders.

If subjects assigned to the ACTIVE FT-CC group are not able to receive text messages due to cellular connectivity or text transmission issues, alternate methods may be used to remind the subject to use their device and will be documented on the Case Report Form (CRF).

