## 16.0 Statistical Methods

### 16.1 Sample Size Determination

No power calculations were used to derive a sample size for this study given this study seeks to identify which health outcomes should be used for a larger randomized controlled trial in the future. The desired target sample size for this feasibility study is 10 analyzable data sets for each group. It is estimated that up to 30 subjects will need to be enrolled to achieve 60 day follow-up data on 20 subjects.

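### Girth, quality of life and symptoms are to be analysed by a compliance category formed after randomisation, with no by-arm summary specified and no caveat on confounding, although the study is meant to inform outcome choice for a larger trial

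*Combined protocol and SAP*

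**What the plan says.** Section 5.1.2 defines two compliance bands in Table 1, average use on 1-4 and on 5-7 days per week, and says of the exploratory endpoints: "These endpoints will be analyzed using the following compliance categories". The endpoints are then worded as the impact of device compliance on girth, quality of life and symptoms, which matches the second objective in section 4.0.

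In Table 2 (section 5.1.3) only the compliance row names PASSIVE and ACTIVE. The girth, quality-of-life and symptom rows name time points only. Section 5.0 gives the reason for randomising: "Randomization was incorporated into the study to determine if ACTIVE FT-CC affects device use". Section 5.5 sets a 1:1 allocation, with text reminders in ACTIVE after two consecutive days without use and none in PASSIVE.

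Section 16.1 explains the absence of a power calculation by saying that "this study seeks to identify which health outcomes should be used for a larger randomized controlled trial in the future". It continues: "The desired target sample size for this feasibility study is 10 analyzable data sets for each group", and "It is estimated that up to 30 subjects will need to be enrolled to achieve 60 day follow-up data on 20 subjects".

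Section 16.2 lists generic descriptive statistics without naming a grouping. It mentions confidence intervals for categorical data only, plans no explicit reporting of missing-data counts, describes no adjustment for baseline differences, and plans no hypothesis tests.

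**The concern.** Compliance category is an outcome of the trial, not something assigned. A woman reaches the higher band through motivation, tolerance of the garment, symptom burden and free time and, if she is in ACTIVE, through the reminders. Any of these may also relate to how her girth or questionnaire scores change. A difference between categories is therefore a confounded association, yet the plan calls it *impact* and adds neither adjustment nor warning.

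This matters because of the use foreseen in section 16.1. If the category tables are the only planned between-group view of the candidate outcomes, an outcome could be carried forward because heavier users differ in other ways. Another could be passed over because one category holds very few women. The figures a planner needs (mean change, SD of change and completion for each outcome, overall and by arm) are not specified anywhere.

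**Working it through.** **The plan's own figure.** Section 16.1 goes from 20 analysable subjects to 30 enrolled. Solving 20/(1 - d) = 30 gives d = 1 - 20/30 = 33.3%, an attrition that the plan does not state. No alpha, power, effect size or SD is given, so there is nothing further to reproduce. The figures below use the 20 analysable subjects (10 per arm).

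**What is specified, by outcome.**

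| Outcome | Grouping specified | Source |
|---|---|---|
| Compliance rate | PASSIVE versus ACTIVE | 5.1.1, Table 2 |
| Girth, LYMQOL ARM, SF-36, LSIDS-A | Compliance category; change over time | 5.1.2, Table 2 |

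**Precision.** With equal SDs, the standard error of a difference between groups of n1 and n2 is SD × √(1/n1 + 1/n2). At 10/10 this is √0.2 = 0.447 SD. The 95% CI half-width is t(0.975, 18) × that, 2.101 × 0.447 = 0.94 SD. The documents give no compliance share, so the other splits are assumptions.

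| Split of 20 | √(1/n1 + 1/n2) | SE relative to 10/10 | 95% half-width (SD) |
|---|---|---|---|
| 10/10 | 0.447 | 1.00 | 0.94 |
| 12/8 | 0.456 | 1.02 | 0.96 |
| 14/6 | 0.488 | 1.09 | 1.03 |
| 16/4 | 0.559 | 1.25 | 1.17 |
| 18/2 | 0.745 | 1.67 | 1.57 |

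The loss is negligible for mild imbalance and serious only if one category is nearly empty. Table 1 also has no band for average use below 1 day per week or between 4 and 5 days, so some subjects could fall outside both groups.

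**Confounding.** Assume that use has no causal effect, but that use and outcome change are bivariate normal with correlation ρ, and let a share q be compliant. With c the cut point and φ the standard normal density, the expected category difference in SD units is ρ × [φ(c)/q + φ(c)/(1 - q)].

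| ρ | q = 50% | q = 70% | q = 80% |
|---|---|---|---|
| 0 | 0 | 0 | 0 |
| 0.2 | 0.32 | 0.33 | 0.35 |
| 0.3 | 0.48 | 0.50 | 0.53 |
| 0.5 | 0.80 | 0.83 | 0.88 |

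Example for ρ = 0.3, q = 50%: c = 0, φ = 0.399, so 0.3 × (0.399/0.5 + 0.399/0.5) = 0.48.

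A simulation of 20,000 trials with 10 per arm kept the zero causal effect and let reminders raise use by 0.5 SD. The category difference averaged 0.47 SD at ρ = 0.3 and 0.78 SD at ρ = 0.5. The by-arm difference averaged 0.00 SD in both. The values of ρ, q and the reminder shift are illustrative; the documents supply none.

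**What a by-arm contrast can deliver.** Both arms use the same device, so the contrast carries only what the reminders change. If reminders shift use by 0.5 SD and each SD of use truly shifts an outcome by 0.5 SD (both assumed), the arm difference is 0.5 × 0.5 = 0.25 SD, against a half-width of 0.94 SD. At 10 per arm, 80% power at two-sided 5% needs about (1.96 + 0.84) × √(2/10) = 1.25 SD. The contrast is unbiased but very imprecise.

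**What pooled change can deliver.** For mean change over all 20 subjects, the half-width is t(0.975, 19)/√20 = 2.093/4.472 = 0.47 SD of change, half that of the arm contrast. It does not depend on compliance category.

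**The case against.** The strongest reply is that the plan follows its own objectives. Section 4.0 asks how compliance affects girth, quality of life and symptoms, section 3.1 gives limited data on that question as the motive, and section 5.0 ties randomisation to device use only. Grouping by compliance implements that objective, and the endpoints are exploratory with no tests planned. All of this stands: the compliance analysis is not the fault, and the primary comparison is untouched.

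Three stronger readings are tempting and are not supported.

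- *The study was sized to choose outcomes and cannot do so.* Section 16.1 contains no sizing calculation. Choosing outcomes is the reason given for omitting one and is not a listed objective. Table 2 also plans baseline to Day 30/60 comparisons, which bear on which outcomes move.
- *Health outcomes will never be summarised by arm.* Section 16.2 leaves the grouping open and does not exclude by-arm tables. They are unspecified, not ruled out.
- *The larger trial would compare ACTIVE with PASSIVE, so the arm contrast should decide which outcomes go forward.* The documents do not say what that trial would compare. The contrast reflects reminders alone and is too imprecise to screen outcomes.

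It is also incomplete to call the categories purely self-selected, since in ACTIVE the reminders act on use. What the reply leaves unanswered is the causal wording without a caveat and the absence of any specified alternative view of these outcomes.

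**Conclusion.** The concern holds in a limited form. The only between-group analysis specified for the health outcomes uses a post-randomisation grouping, described causally and without adjustment, in a study that says it will inform outcome choice for a larger trial.

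Under the assumed correlations of 0.2 to 0.5, confounding alone gives category differences of roughly 0.3 to 0.9 SD. Imbalance inflates the standard error by 2% at 12/8 and by 67% at 18/2. These sizes rest on illustrative inputs; the structural point does not. The change is worth making because it guards against a misleading reading at almost no cost. It is not a defect that invalidates the study or its primary endpoint.

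**What to change.** Amend section 5.1.2, Table 2 and section 16.2 as follows.

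- (a) For girth, the LYMQOL ARM domains, the SF-36 scales and LSIDS-A, summarise change from baseline to Day 30 and Day 60 by randomised arm as assigned: n, mean, SD, and the ACTIVE minus PASSIVE difference with a 95% CI.
- (b) For each outcome, add the standardised response mean pooled over arms (mean change/SD of change) and the completion rate. Name these, with the per-arm SDs, as the main inputs for choosing outcomes. Completion has to be added explicitly because section 16.2 does not plan to report missing-data counts.
- (c) Keep the compliance-category tables, label them as non-randomised associations, replace the causal wording, and show baseline characteristics by category.
- (d) State the limits. The arm contrast estimates the effect of reminders only, with a half-width of about 0.94 SD at 10 per arm, and a null contrast is not a reason to drop an outcome. Pooled change has no untreated comparator, so it describes movement during device use and not an effect of the device.

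The cost is wording and one extra set of tables from data already collected. No additional subjects, visits or hypothesis tests are needed.

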#### **5.4 Subject Discontinuation or Withdrawal**

Subject participation may be discontinued prior to study completion for any of the following reasons:

- **Withdrawal of Consent**  
Subjects may withdraw their consent to participate at any time. If a subject withdraws consent, previous information that has already been obtained will be available for analysis.
- **Discretion of the Principal Investigator**

Subjects may be withdrawn at the investigator's discretion in the event of changes in the subject's health, or other reasons based on the investigator's clinical judgment.

When a subject withdraws prior to completing the study, the reason for withdrawal will be recorded.

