### 7.7 Lymphedema Treatment Review

During each visit, with the exception of the training visit, the subject will also be asked questions regarding their use in the last 7 days of the FT-CC (Day 30 and 60 only), compression garments, and other prescribed lymphedema treatment.

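### Table 1 gives no compliance category to women averaging under 1, or between 4 and 5, days of use a week, and the comparison built on it shows association rather than impact

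*Combined protocol and SAP*

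**What the plan says.** The second aim in section 4.0 is causal in wording: "Identify the impact device compliance has on arm girth, quality of life, and symptoms". Section 5.1.2 carries it out through Table 1, which has two rows. Partially Compliant is "FT-CC used on average 1-4 days per week" and Compliant is "FT-CC used on average 5-7 days per week". The text introducing the table says: "These endpoints will be analyzed using the following compliance categories". There is no third category, no rounding rule and no stated averaging window.

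Table 2 (section 5.1.3) defines the compliance rate for the primary endpoint as days used over total study days, at 30 and 60 days. Its girth row reads "Comparison between baseline and day 30/60 arm girth measurement" and mentions neither category nor arm.

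Section 16.1 expects 60-day data on 20 women from up to 30 enrolled. Section 16.2 plans descriptive statistics and no formal tests. It plans no imputation and no tabulation of missing counts, and it names no summary of girth, quality of life or symptoms by randomised arm.

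**The concern.** Two things are at stake.

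First, the rule does not say where every woman belongs. A woman who misses every third day uses the device on 40 of 60 days, or 4.67 days a week. She is a fairly regular user, yet she has no category. With single-day gaps she would never trigger the two-day reminder either. At the other end, a woman who stops in the first week but stays in follow-up also has no category. Because section 16.2 does not tabulate missing counts, such losses would show only as differing sample sizes between tables. If the women are instead placed after the data are seen, that choice can move a comparison based on about 20 women.

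Second, what is randomised is the reminder, not the amount of use. Use builds up over the same weeks as the change in girth and symptoms, and a woman may use the device less because her arm swells or hurts. A difference between the categories can therefore reflect the effect of use, the cause of low use, or both. This matters because section 16.1 says the study is meant to help choose health outcomes for a larger trial.

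**Working it through.** **Inputs from the documents.** Category bounds: 1-4 and 5-7 days a week (Table 1). Follow-up: 30 and 60 days (section 5.5, Table 2). Women with 60-day data: 20 of up to 30 enrolled (section 16.1; 20/30 implies a loss of one third, which is not disputed here). The plan gives no figure for the categories themselves to reproduce.

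**Step 1: which counts have no category.** With k days used out of T, average days a week = 7k/T.

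| T | Below 1 a week | Between 4 and 5 a week | Counts with no category |
|---|---|---|---|
| 60 | 0-8 (8 gives 0.93; 9 gives 1.05) | 35-42 (34 gives 3.97; 35 gives 4.08; 42 gives 4.90; 43 gives 5.02) | 9 + 8 = 17 of 61 |
| 30 | 0-4 (4 gives 0.93; 5 gives 1.17) | 18-21 (17 gives 3.97; 18 gives 4.20; 21 gives 4.90; 22 gives 5.13) | 5 + 4 = 9 of 31 |

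The ±7 day window at Day 60 moves the gaps slightly: 0-7 and 31-37 of 53 days, or 0-9 and 39-47 of 67 days.

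**Step 2: what rounding would do.** If averages were rounded to whole days, 35-38 of 60 (4.08-4.43) would become Partially Compliant and 39-42 (4.55-4.90) Compliant. Counts of 0-4 (4 gives 0.47) would round to 0 and still have no category.

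**Step 3: how many women.** The distribution of use is an assumption. Take the share of days used as beta-distributed with cumulative function F. Expected women with no category = 20 × [F(8.5/60) + F(42.5/60) − F(34.5/60)].

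| Mean use | SD between women (percentage points) | Women of 20 with no category |
|---|---|---|
| 50% | 15-30 | 4.7 to 5.7 |
| 60% | 15-30 | 4.3 to 6.5 |
| 70% | 15-30 | 3.3 to 5.5 |
| 80% | 15-30 | 2.2 to 3.0 |
| 90% | 15-25 (30 not attainable) | 1.1 to 1.4 |

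A separate beta-binomial calculation (mean 50-80%, concentration 2-8) gives 2.2 to 5.6 of 20. With rounding, the first model leaves 0 to 1.8.

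**Step 4: whether the bias can be sized.** Suppose use has no effect on girth, mean use is 70% (beta, concentration 4), and use correlates with the underlying swelling trend at −0.2, −0.3 or −0.5. The Compliant group then shows a girth change lower by 0.39, 0.59 or 0.97 SD. If women with more swelling use the device more, the correlation changes sign and so does the difference. At zero correlation it is zero.

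For comparison, this model puts 53.7% of women in Compliant and 25.3% in Partially Compliant, or 10.7 and 5.1 of 20. The standard error of the difference is √(1/10.7 + 1/5.1) = 0.54 SD. All three values are under two standard errors. The documents give none of these correlations, so this step shows only that a contrast can arise without any effect of use.

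**The case against.** The strongest reply is that these endpoints are exploratory, that section 16.2 limits the study to estimation and hypothesis generation, and that a descriptive association serves that purpose. A sensible analyst would round, carry the Table 2 denominator over to Table 1, and read the girth row of Table 2 as allowing an overall summary of change. All of that is reasonable. It lowers the stakes but does not close the gap: rounding is not written down, very low use would still have no category, and estimation needs to know who is in each group.

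A reader might also infer more than the documents support:

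- **That swelling will drive women to stop, because section 9.0 lists increased swelling and pain as likely reactions.** The same section calls the therapy minimal risk and places the probability of these device risks at the lowest level. It gives no rate.
- **That the reasons for low use go unrecorded.** Section 5.4 covers only women who leave: "When a subject withdraws prior to completing the study, the reason for withdrawal will be recorded". But section 7.14 has adverse events assessed from randomisation throughout the study, section 7.14.4 records device observations, and section 5.5 says of changes to settings that "these modifications will be documented". Section 7.7 also asks about recent use at Day 30 and Day 60. What is missing is an explicit link between an event and reduced use, which is a small matter.
- **That the sign of the comparison could reverse with the denominator.** That needs days counted only until use stops, contrary to the one denominator the plan states.

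**Conclusion.** The point holds as a fault in a stated rule, together with a correction of wording. The gaps in Table 1 (0-8 and 35-42 of 60 days; 0-4 and 18-21 of 30) follow from arithmetic and need no assumption. The number of women affected, about 1 to 6 of 20, rests on assumed distributions of use and falls to 0 to 1.8 if an unstated rounding rule is applied.

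That the category comparison cannot by itself show an impact follows from the design, since use is self-selected after randomisation and may respond to swelling or pain. It would go too far to say that the comparison is biased by a given amount, or that it favours compliance: neither size nor direction can be derived from the documents, and the illustrative values are within sampling noise for a study of this size. The primary endpoint compares days used over total study days by randomised arm, does not use Table 1, and is unaffected.

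**What to change.** 1. In Table 1, use categories that cover every value: below 1, 1 to below 5, and 5 to 7 days a week. Over 60 days these are 0-8, 9-42 and 43-60 days used, so all 9 + 34 + 18 = 61 counts are classified.
2. State that the average uses the Table 2 denominator: total study days up to the visit, including days after use stops.
3. In section 16.2, summarise change in girth, quality of life and symptoms at Day 30 and Day 60 for all women with data, overall and by randomised arm, alongside the category comparison.
4. Describe the category comparison as an association, not an impact, in sections 4.0 and 5.1.2 and in the synopsis.

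The cost is a revised table, a few sentences, and summary tables from data already collected. No new visit or form is needed.

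There are limits. Exhaustive categories settle who is counted but do not remove self-selection, which is why items 3 and 4 are needed as well. By-arm summaries with about 10 women per group are imprecise: the standard error of the difference is √(1/10 + 1/10) = 0.45 SD. They also reflect the effect of reminders rather than of use, so they complement the category comparison and do not replace it.
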